Objectives	
Primary Objective:
 
The primary objective will be to determine the efficacy of NOVOTTF-200A in recurrent anaplastic astrocytoma patients (6-month progression-free survival)
 
Secondary Objectives:
 
 • To evaluate the safety of NOVOTTF-200A in the subject population. • To evaluate efficacy of NOVOTTF-200A in the subject population. • To see if the presence of ATRX, TERT promoter, IDH1 mutations and/or MGMT promoter methylation, confers a better response to NOVOTTF-200A. • To determine if the treatment significantly modifies the patient’s quality of life. We will use the Functional Assessment of Cancer Therapy (FACT) questionnaires: 
 ○ FACT-Brain (FACT-Br) ○ FACT-Cognitive Function (FACT-Cog) 
Exploratory Objectives:
 
 • To determine if the presence of proneural or mesenchymal phenotype (Cytoscan analysis) confers a better response to NovoTTF. • To determine if the in vitro sensitivity of the glioma cells derived from patient specimens before and after the NOVOTTF-200A treatment correlates with the patient’s response to treatment.
Study Design	
This is a Phase 2 study in subjects with WHO Grade III Anaplastic Astrocytoma (G3 astrocytoma) who had progressive disease during first or second line treatment and who have not previously received any BEV or any experimental agents.
 
Up to 36 subjects will be enrolled and will be used to assess efficacy. Given the nature of the NOVOTTF-200A device, no cohort will be needed to assess maximum tolerated dose (MTD) as it does not apply.

Study Treatments	
NOVOTTF-200A has received FDA approval for other indications and will be available through a commercial use program by NovoCure.

	NOVOTTF-200A will be administered under appropriate guidelines. Monthly adherence rate $\geq 75\%$ (≥ 18 hours/day) over a 4-week cycle (28 days) will be strongly encouraged.
No. Subjects	Up to 36 subjects will be enrolled in the study (26 evaluable needed).

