3. OVERALL STUDY DESIGN

3.1. Study Design

This is a Phase 2, single arm study in subjects with AA who had progressive disease during first-line treatment or who are in first or second relapse and who have not previously received any bevacizumab (BEV) or other anti-angiogenic agent, including sorafenib, sunitinib, axitinib, pazopanib or cilengitide. Up to 36 subjects will be enrolled with 26 evaluable patients needed.

The determination of whether to stop treatment due to progression will be based on the investigator's evaluation of the patient's clinical condition. NovoTTF-200A treatment may be continued until disease progression, unacceptable toxicity, withdrawal of consent, or termination of the study. In the case of radiological progression, NOVOTTF-200A treatment will be stopped and a different treatment will be chosen instead by the investigator.

Patients will be recruited to the study by the principal investigator (PI) or one of the coinvestigators (CI) at UC Irvine. Patient accrual is expected to continue for 24-36 months.

NovoTTF-200A treatment will be given alone for this single arm study. At treatment initiation patients will be seen at an outpatient clinic. During this visit baseline examinations will be performed and NovoTTF-200A treatment will be initiated under medical supervision. The patients will also be instructed on the operation of the NovoTTF-200A and battery replacement. Once the patients are trained in operating the device they will be released to continue treatment at home. The patients will receive multiple 1 month courses of continuous NovoTTF-200A treatment.

NovoTTF-200A treatment will be stopped in the following cases:

1. Treatment will be stopped in the case of device related serious adverse events
2. Clinical and functional deterioration considered by the investigator to be prohibitive of continuing treatment.
3. Radiological progression
4. Re-operation, for the patients where the pathology is consistent with necrosis (pseudo-progression). NovoTTF-200A treatment will be interrupted for at least 2 weeks after reoperation or until wound healing).

As long as the patients are receiving treatment (NovoTTF-200A), all patients will be seen once every month at an outpatient clinic where they will undergo medical follow-up and routine laboratory exams. An MRI will be performed every second month following the baseline MRI.

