5.1. Number of Subjects and Sites

Approximately 36 subjects will be enrolled in the study 26 evaluable patients needed.

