8. STATISTICAL CONSIDERATIONS

Efficacy: Tumor response, including PD, progression-free survival (PFS), and overall survival (OS) will be assessed. Tumor response will be assessed by the Investigators using RANO 2010 criteria. The overall confirmed response rate will be presented. Primary outcome variable will be 6-month PFS. In addition, response rate will also be measured taking into account partial response and complete response.

Primary Objective: The primary objective is to estimate the proportion of participants showing no evidence of disease progression six months after initiating treatment with the device (PFS₆). We will compute interval estimates of this proportion. This information will inform decisions about further research on this device (or similar approaches). We will also document issues of intolerability and all adverse events.

Primary Efficacy Endpoint: The primary efficacy endpoint is disease status six months from initiation of treatment with the device. Assessment is per RANO (2010) criteria. The primary efficacy measure is the 90-percent interval estimate of PFS₆.

Primary Adverse Event Measures. Adverse events will be recorded, including time-on-treatment and an assessment of likely relation to device use. Reasons for discontinuing use of the device will be recorded to the fullest extent possible.

Analysis Data Sets for Efficacy: The primary efficacy analyses will be conducted on the intent-to-treat data set (ITT), defined as including all participants receiving at least one exposure to the active device. Supplemental analyses will be performed on the per-protocol data set (PP), defined as including only those participants meeting the minimum prescription for device use (≥ 18 hours daily over a four-week cycle).

Variables to be Collected. In addition to adverse events, reasons for discontinuation, disease trajectory, mutation status (viz., ATRX, TERT, IDH1, MGMT), Karnofsky performance status, and psychometrics (viz., FACT-Br, FACT-Cog), information on patient demographics, host factors, and co-morbidities will be collected for use in exploratory analyses. Survival will be tracked until death or the end of the project. Information on further anti-glioma treatments received after patients are off of this study will be sought.

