Design: This is a single-center, single-arm, open-label, Phase-IIA clinical trial to estimate PFS₆ under the conditions of the trial and to gather information on safety and tolerability associated with the device in clinical use.

8.1. Sample Size: Justification of Sample Size: Data from 36 participants will yield a 90-percent interval estimate of PFS₆ with sufficient precision for our purposes. Table 1 shows the probability of observing a 90-percent confidence interval from 34 participants at various levels of the population proportion and confidence-interval half widths. The table is based on 34 rather than 36 participants, anticipating some loss of participants to the exigencies of research.

The table shows over 90-percent power to estimate PFS₆ to plus or minus 16 percent at all levels of the population proportion shown. The power to estimate PFS₆ to plus or minus 15

percent is adequate for the more extreme levels of population proportion, but perhaps not when the latter is near 50 percent.

Table 1. Probability of Observing a 90-Percent Binomial Confidence Interval Given 34 Subjects for the Indicated Underlying True Proportions and Interval Half Widths

Population Proportion	Interval Half-Width		
	13%	15%	16%
25%	0.36	0.99	0.99
35%	0.05	0.83	0.99
45%	0.00	0.47	0.99
55%	0.00	0.47	0.99
65%	0.05	0.83	0.99
75%	0.36	0.99	0.99

Rounded to nearest one hundredth, exact method, 2-sided, SAS Power and Sample Size v3.1

Futility Assessment. If none of the first nine participants is progression-free at six months from initial use of the device, then serious consideration will be given to stopping the project for futility. This criterion is adopted from the Simon, two-stage, optimal design (null-hypothesis rate of 5% v alternate- hypothesis rate of 25%). A formal decision to stop the trial will depend upon the clinical judgment of the medical director.

Intolerability Assessment. Intolerability and adverse events will be closely monitored by the treating physicians. A decision to stop the project for intolerability will be based on clinical judgment of the medical director.

Primary Analyses for Efficacy: The 90-percent interval estimate of PFS6 is the primary summary of efficacy in this project. Exact methods will be used.

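### The 26 evaluable patients said to be needed are undefined and unsupported: Section 8.1 justifies its precision for 34 of 36, and at 26 the stated ±16% would usually be missed

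*Combined protocol and SAP*

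**What the plan says.** Section 8 makes the interval the primary result: "The primary efficacy measure is the 90-percent interval estimate of" PFS6. Under the primary analyses in Section 8.1 it adds "Exact methods will be used". Section 8 also fixes the primary analysis set, labelled ITT, as everyone exposed to the active device at least once.

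The sample-size justification in Section 8.1 starts from 36 participants and tabulates precision on fewer: "The table is based on 34 rather than 36 participants, anticipating some loss of participants to the exigencies of research". The table footnote gives the method: "Rounded to nearest one hundredth, exact method, 2-sided, SAS Power and Sample Size v3.1". From the table the section concludes that there is over 90% power to estimate PFS6 "to plus or minus 16 percent at all levels of the population proportion shown". It is more guarded about ±15% when the true proportion is near one half.

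Three other places give a different number:

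- Synopsis, No. Subjects: "Up to 36 subjects will be enrolled in the study (26 evaluable needed")
- Section 3.1: "Up to 36 subjects will be enrolled with 26 evaluable patients needed"
- Section 5.1: "Approximately 36 subjects will be enrolled in the study 26 evaluable patients needed"

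The number 26 does not appear in Section 8, and no section defines *evaluable*.

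**The concern.** Section 8.1 allows for losing 2 of 36 participants (2/36 = 5.6%). The other three places tolerate a loss of 10 of 36 (10/36 = 27.8%). These are different planning assumptions, and only the first has a calculation behind it.

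This matters because the trial has one arm and no hypothesis test on the primary endpoint. The 90% interval is the main efficacy result, and its expected width is the only justification offered for the sample size. With enrolment set at up to 36 and 26 given as the number needed, a team could close near 26 and believe it had met the protocol, at a size for which the plan gives no precision.

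The most affected values of PFS6 are those near one half. The protocol's own background figures lie there: 55% and 56% for bevacizumab-based treatment of grade III disease (synopsis and Section 1.1), and 50% in the device pilot in recurrent glioblastoma (Section 1.2).

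**Working it through.** **Inputs.** Two-sided 90% interval, exact binomial method (Section 8.1 and its table footnote); n = 34 (Section 8.1); n = 26 (synopsis, Sections 3.1 and 5.1); n = 36 (planned enrolment); true proportions 25% to 75% in steps of 10 points (the table in Section 8.1).

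**Formulas.** For x progression-free out of n, the exact (Clopper-Pearson) limits are

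- L(x) = 0.05 quantile of Beta(x, n − x + 1), with L(0) = 0
- U(x) = 0.95 quantile of Beta(x + 1, n − x), with U(n) = 1
- half-width w(x) = (U(x) − L(x))/2

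The probability of achieving half-width h at true proportion p is the sum of the Binomial(n, p) probabilities over all x with w(x) ≤ h.

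**Step 1: reproduce the plan's table at n = 34.**

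| True PFS6 | ≤13%: plan / recomputed | ≤15%: plan / recomputed | ≤16%: plan / recomputed |
|---|---|---|---|
| 25% or 75% | 0.36 / 0.357 | 0.99 / 0.988 | 0.99 / 1.00 |
| 35% or 65% | 0.05 / 0.053 | 0.83 / 0.830 | 0.99 / 1.00 |
| 45% or 55% | 0.00 / 0.003 | 0.47 / 0.468 | 0.99 / 1.00 |

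The table reproduces. The widest interval at n = 34 occurs at x = 17, where w = 15.1 points, so ±16% is met whatever is observed. The printed 0.99 in that column is harmless.

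**Step 2: the same calculation at n = 26.** Around the 16-point threshold, w(7) = 15.65 and w(8) = 16.19 points. The half-width is therefore at most 16 points only if x ≤ 7 or x ≥ 19.

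| True PFS6 | P(w ≤ 15%) | P(w ≤ 16%) | P(w ≤ 17.5%) |
|---|---|---|---|
| 25% or 75% | 0.52 | 0.69 | 1.00 |
| 35% or 65% | 0.14 | 0.26 | 1.00 |
| 45% or 55% | 0.02 | 0.05 | 1.00 |

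No row reaches 0.90 for ±16%.

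**Step 3: how much wider the interval becomes.** The worst-case half-width over all outcomes is:

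| n | Worst-case half-width (points) |
|---|---|
| 26 | 17.3 |
| 30 | 16.1 |
| 31 | 15.8 |
| 34 | 15.1 |
| 36 | 14.7 |

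The step from 34 to 26 adds 17.3 − 15.1 = 2.2 points at worst. The expected half-width rises from 13.1 to 15.0 points at a true PFS6 of 25%, and from 14.8 to 17.0 at 45%. The smallest n at which every outcome meets ±16% is 31.

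**The case against.** A reader might infer that the plan's precision claim is false, or that the protocol promises ±16% from 26 patients. The documents support neither. Section 8.1 ties the claim to 34, where it is correct, and the three passages that mention 26 say nothing about precision or about stopping enrolment there.

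The only denominator named for the primary analysis is all exposed participants. If 34 to 36 are exposed and all are counted, the ±16% claim holds even if only 26 are evaluable in some other sense. This stands, and it makes the shortfall conditional. It does not settle the matter. *Needed* reads as a minimum, *evaluable* has no meaning in the text, and Section 8 does not say how an exposed participant without a six-month assessment is counted. Nothing excludes closing near 26 or computing the proportion on 26.

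It can also be said that the fall in probability exaggerates the loss. That is right: at 26, exact half-widths for mid-range outcomes lie just above 16 points, so a small widening moves most of the probability across the threshold. No pre-specified decision turns on ±16%, and Section 8.1 reports it as a property of the design, not as a requirement.

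Finally, other interval methods would stay within 16 points at 26: Wilson and Agresti-Coull reach at most 15.4 and Jeffreys 15.6. Section 8.1 commits to exact methods, so these do not rescue the figure as planned.

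**Conclusion.** The point holds as an internal inconsistency in the sample size, not as an arithmetic error, and it ranks below must-fix. The minimum of 26 evaluable patients is undefined and underived, and it conflicts with the 34 of 36 on which the precision rests.

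If 26 became the denominator of PFS6 or the point at which accrual closed, the probability of a half-width within 16 points would be 0.05 to 0.69 instead of over 0.90, while the worst-case interval would be ±17.3 points instead of ±15.1.

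This rests on the planned exact two-sided 90% interval, on the range of true PFS6 that the plan tabulates, and on one of those two conditions occurring. With 34 or more exposed participants all counted, the claim in Section 8.1 stands.

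**What to change.** State in Section 8 and the synopsis that the denominator for PFS6 is all exposed participants. Then choose one of the following and use it consistently in the synopsis and Sections 3.1, 5.1 and 8.1:

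- **(a)** Delete the statement that 26 evaluable patients are needed from the synopsis and Sections 3.1 and 5.1, and report worst-case half-widths of 15.1 points at n = 34 and 14.7 points at n = 36.
- **(b)** Keep 26, define *evaluable*, and state in Section 8.1 that at 26 the exact 90% interval is within ±17.5% for every outcome.

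If ±16% is to be kept for every outcome, the stated minimum in the primary analysis should be 31, which is within the planned 36.

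The cost is wording in a few places, with no additional patients beyond those planned. Under (b) the stated precision is slightly less favourable. The choice should be made before PFS6 is analysed, so that the denominator is not chosen with the results in view.

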Investigational Product/ Background	NOVOTTF-200A will be administered with a monthly adherence rate goal of $\geq 75\%$ (≥ 18 hours daily) of therapy over a 4-week cycle in subjects with recurrent G3 MG who have not previously been treated with any anti-

Therapy/ Route/ Regimen	angiogenic agent including BEV.
Procedures	
Study visits and procedures will be performed as outlined in Table 1.
 
The study will consist of Screening, Treatment and Follow-Up periods.
 
Screening:
 
The screening period may not exceed a 28-day window prior to start of study treatment (Cycle 1, Day 1). Assessments will include medical history, cancer history including previous treatments, physical examination and tumor assessments. Tumor assessment must have a baseline MRI scan with contrast within 14 (+3) days prior to first treatment with investigational product. Vital signs measurement and laboratory tests are to be conducted within 7 days prior to Cycle 1, Day 1.
 
Treatment:
 
Subjects may continue on study treatment until disease progression, unacceptable toxicity, withdrawal of consent or termination of the study. Assessment will include MRI scans at the end of every even numbered cycle (± 7 days) using RANO (2010) criteria for assessment. Subjects who discontinue study therapy for reasons other than disease progression whenever possible will continue tumor assessment as per protocol schedule until progression.
 
Safety Follow-Up (End-of-Treatment Visit):
 
Subject will be followed for safety for 28 (+3) days after discontinuation of trial therapy (NOVOTTF-200A)
 
Survival Follow-Up:
 
All subjects will be followed in the long-term survival follow-up period for as long as they are alive. Long-term follow-up will occur every 3 months (± 7 days) after the 28-day post-treatment discontinuation visit. Telephone contact will be sufficient to document survival status. During the follow-up period, the following information will be collected: survival, and subsequent anti-malignant glioma regimens (regimen, start and end date and treatment outcome).

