In the case of clinical progression an unscheduled MRI will be obtained within 1 week of the investigator becoming aware of the clinical progression. No additional MRIs will be required after progression.

Medical follow-up will continue for 2 months after treatment termination in order to capture treatment related toxicities. After these visits, mortality will be assessed based on monthly telephone interviews with the patients or the patients' caregivers.

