4. PROCEDURES

Study visits and procedures will be performed as outlined in Table 1.

The study will consist of Screening, Treatment, and Follow-up periods.

Screening:

Screening procedures may not be done prior to the signing and dating of the Informed Consent document. However, the results of tumor assessments done as part of standard of care that are within the 14-day screening period do not have to be repeated. However, if results are not available, then tumor assessments are to be conducted within 14 days prior to Cycle 1 Day 1. The screening period may not exceed a 28 day (with a 3 day window for scheduling conflicts) window prior to start of study treatment (Cycle 1 Day 1) for assessments that include medical history including demographics and cancer history, prior medications and procedures. Physical examination including height, weight, and vital signs, electrocardiograms, laboratory tests including hematology, coagulation, chemistry, urinalysis, and, as appropriate, pregnancy tests are to be done within 7 days prior to Cycle 1 Day 1.

Treatment:

Safety tests and procedures will be performed according to the Schedule of Assessments and Procedures (Table 1). Assessments will include MRI scans at the end of every even numbered cycle using RANO 2010 criteria for assessment.

Subjects may continue on study treatment until disease progression, unacceptable toxicity, withdrawal of consent, or termination of the study.

End-of-Treatment Visit:

An End-of-Treatment Visit should occur when a subject discontinues study treatment 28 (+7) days after NOVOTTF-200A. Tests are primarily to ensure there are no late occurring AEs and that AEs have resolved or have stabilized. Additional follow up visits may be conducted to follow ongoing that are resolving. If a subject cannot or will not make this visit, attempts to gather information on the status of AEs should be made by telephone or other means.

Post Study Follow-up:

All subjects will be followed for survival during the follow-up period for as long as they are alive. Post Study follow-up will occur every 3 months (± 7 days) after the End-of-Treatment Visit. During long-term follow-up, the following information will be collected: survival, subsequent anti-glioma regimens, and treatment outcomes.

Efficacy Assessments

Tumor response, including progressive disease, will be assessed with MRI at the end of every 2 cycles of therapy according to the RANO criteria (Wen 2010), including:

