Secondary Analyses for Efficacy: We will examine the data in many ways to inform decisions about further research, including plots, tables, and statistical tests, accounting for repeated measures where appropriate. Participants will be described by sex, age, and other host or clinical factors, using means, medians, and percentiles for continuous variables and counts and percentages for categorical variables. The FACT-Br and FACT-Cog will be scored in the standard way (Weitzner et al, 1995). Both progression-free and overall survival will be estimated by Kaplan-Meier methods, both overall and by strata of interest. Differences in survival between or among groups will be evaluated by the log-rank test. If the assumptions are reasonably met, then Cox proportional-hazards models will examine the effects on survival of covariates adjusting for other covariates. Ties in survival time will be broken by the subtracting a small, randomly generated amount from each tied observation (Borucka, 2014). Secondary analyses will be performed on both the ITT and PP data sets, as seems warranted. For secondary analyses, the probability values from statistical tests will be used as a guide to interpretation, which will also depend on clinical judgment. Therefore, we will not be concerned with overall, study-wise, type-1 error rates for the secondary analyses.

Analyses for Intolerability or Toxicity: We will examine the data to discover factors that may predict adverse reactions to the study treatment. We will proceed in the same way as outlined

above for secondary analyses for efficacy. As the goals of these analyses are to inform decisions about future research, no formal statistical hypothesis testing will be done, probabilities from statistical tests will augment clinical judgment in interpretation, and we will not regard overall, study-wise, error rates.

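### Random tie-breaking with no seed or averaging rule makes the secondary Cox results depend on the draw; naming the Efron method removes this at no cost

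*Combined protocol and SAP*

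**What the plan says.** Section 8.1 (Secondary Analyses for Efficacy) sets out the time-to-event methods in order:

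- Estimation: "Both progression-free and overall survival will be estimated by Kaplan-Meier methods, both overall and by strata of interest". Group differences are then tested by the log-rank test.
- Regression, provided the assumptions are reasonably met: "then Cox proportional-hazards models will examine the effects on survival of covariates adjusting for other covariates".
- Ties: "Ties in survival time will be broken by the subtracting a small, randomly generated amount from each tied observation". A methods paper on tied events in Cox models is cited.

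The plan gives no seed, amount, distribution, number of draws, averaging rule or sensitivity analysis. It does not say whether the altered times also feed the Kaplan-Meier and log-rank analyses. The same paragraph says that secondary p-values guide interpretation alongside clinical judgement, with no study-wise error control.

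The scan schedule bears on how many ties to expect. In the synopsis (Procedures): "Assessment will include MRI scans at the end of every even numbered cycle (± 7 days) using RANO (2010) criteria for assessment". In Section 4: "Assessments will include MRI scans at the end of every even numbered cycle using RANO 2010 criteria for assessment", with no window. The synopsis (Study Treatments) gives a 28-day cycle. Some progressions will be found off schedule. Section 3.1: "In the case of clinical progression an unscheduled MRI will be obtained within 1 week of the investigator becoming aware". The unit in which PFS is recorded is not stated.

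**The concern.** The Cox partial likelihood depends on the order of events. When two patients with different covariate values share an event time, a random subtraction decides which comes first, and the fitted hazard ratio moves with that decision. Two analysts holding the same locked data could both follow the plan and report different hazard ratios and p-values.

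PFS is where this could matter. Scheduled scans are 2 × 28 = 56 days apart, so if times are recorded by cycle, by month or by nominal scan date, most events share a time with another. With about 34 patients, reordering a handful of them can be visible in the result.

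The wording also covers each tied observation, not each tied event. Read literally, a patient censored on the date of another patient's progression could be moved ahead of that event and drop out of its risk set.

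**Working it through.** **The plan's own figure.** The documents give no figure for the Cox models or for tie handling. The related stated figure is the precision table in Section 8.1, based on 34 patients. It reproduces with Clopper-Pearson 90% intervals: for a true proportion of 45% and a half-width of 15%, 0.468 against the stated 0.47. All cells agree to within 0.01. I therefore take n = 34 below. That interval uses a binary status at six months, so tie-breaking does not enter it.

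**Why order matters.** Take 34 patients split 17/17 on a marker (assumed), with HR 0.5 (assumed). The risk-set total is 17 × 0.5 + 17 × 1 = 25.5. Suppose one patient from each group progresses at the first scan. The denominator of the partial likelihood is then:

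- marker-positive first: 25.5 × (25.5 − 0.5) = 637.5
- marker-negative first: 25.5 × (25.5 − 1) = 624.75
- Efron: 25.5 × (25.5 − 0.5 × (0.5 + 1)) = 25.5 × 24.75 = 631.125

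Random subtraction picks one of the first two. Efron gives a single value, here exactly midway between them.

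**Two example data sets.**

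- Nominal 56-day grid, 31 events, up to 7 at one time: Efron HR 0.347, p = 0.0062. Over 500 random tie-breaks, HR ran from 0.30 to 0.39 and p from 0.0023 to 0.0152.
- Calendar days spread over ±7 days, 30 events: Efron HR 0.408, p = 0.023. Random tie-breaks gave HR 0.404 to 0.413 and p 0.0216 to 0.0250.

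**Simulation.** Assumptions not in the documents: exponential PFS, PFS6 of 25% or 50%, marker split 17/17, HR 0.5, scans every 56 days, no progression found between scans, no early dropout, and a subtraction uniform on 0 to 0.5 time units. Each row rests on 120–150 data sets with 25–30 draws each. The value 0.05 is only a yardstick.

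| PFS recorded as | PFS6 | Events tied | SD of log HR across draws ÷ its SE | Median max/min HR | p on both sides of 0.05 |
|---|---|---|---|---|---|
| Nominal scan date | 25% | 93% | 0.17 | 1.28 | 25% |
| Nominal scan date | 50% | 90% | 0.11 | 1.17 | 16–19% |
| Whole months | 25% | 89% | 0.16 | 1.25 | 27% |
| Whole months | 50% | 84% | 0.09 | 1.13 | 14% |
| Whole weeks | 50% | 67% | 0.05 | 1.07 | 7% |
| Days, scans within ±1 | 25% | 79% | 0.08 | 1.12 | 12% |
| Days, scans within ±1 | 50% | 66% | 0.05 | 1.07 | 7% |
| Days, scans within ±3 | 50% | 39% | 0.03 | 1.03 | 5% |
| Days, scans over ±7 | 25% | 34–36% | 0.02 | 1.02–1.03 | 3% |
| Days, scans over ±7 | 50% | 22–23% | 0.01 | 1.01 | 1–3% |

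**Dependence on the true HR.** HR 0.5 is close to the worst case. With 31 events split evenly, the expected Wald statistic is |ln 0.5| × √(31/4) = 0.693 × 2.784 = 1.93, almost at 1.96. A run of 300 data sets, with PFS6 40% in the reference group, gave these shares on both sides of 0.05:

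| True HR | Nominal grid | Days over ±7 |
|---|---|---|
| 0.3 | 6% | 0.7% |
| 0.5 | 13% | 3% |
| 0.7 | 11% | 1.7% |
| 1.0 | 7% | 1% |

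Other runs gave 16–20% at HR 0.5 and 5% at HR 1 on the grid. With scan-day times they gave between 0–1% and 4–6%. Taking all runs together, the range is about 5–27% for the grid or months and about 0–6% for calendar days within the ±7-day window.

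**Bias.** On the nominal grid, the mean log HR was −0.759 with random tie-breaking and −0.755 with Efron (PFS6 50%), and −0.698 against −0.687 (PFS6 25%). In a separate run of 600 data sets, the median HR was 0.50 for both, and 0.54 for Breslow.

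**The case against.** The strongest reply is that very little is at stake. Most of it stands.

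- *Ties may be few.* A reader might infer from the 8-week schedule that PFS times must be heavily tied. The documents do not say so. The synopsis allows ±7 days, Section 3.1 brings in unscheduled scans at clinical progression, and Section 7.2 counts other antitumour medication as progression on whatever date it occurs. Off-schedule progressions were left out of the simulations and would lower the tie counts further.
- *The noise is small.* At its largest in the table, the draw adds about 0.17² = 2.9% to the variance of log HR. Over the full ±7-day window it adds about 0.02² = 0.04%. There is no clear bias.
- *The marker analyses do not rest on these models.* A reader might infer that they do. Section 8.1 assigns group differences to the log-rank test, which needs no tie-breaking. The Cox models are conditional and serve covariate adjustment, and Section 9.1 calls the marker outcome correlations.
- *No threshold is set.* The plan attaches no decision to p = 0.05 in these analyses.
- *Censored times may not be moved.* The cited paper concerns tied events, which favours an events-only reading. The effect was not quantified.
- *A recorded seed would restore reproducibility.* That is true, but the plan does not call for one, and the reported value would still be one arbitrary draw.

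None of these points gives a reason to prefer a random method to a deterministic one that gives the same answer on average.

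**Conclusion.** The point holds as a free improvement. As written, the tie rule makes the secondary Cox hazard ratios and p-values depend on an unspecified random draw, and the plan alone does not allow them to be reproduced.

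The size depends on an unstated choice. If PFS is kept on the nominal grid or in months, roughly 5–27% of simulated data sets gave p-values on both sides of 0.05. If calendar days are spread within the ±7-day window, about 0–6% did. These figures rest on n = 34, a binary marker and the assumed PFS distributions and hazard ratios above.

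It would be wrong to conclude that the trial's efficacy result is in doubt or that the Cox estimates are biased. The exact 90% interval for PFS6 does not use these times, OS by date of death should have few ties, and random and Efron estimates agree on average. The shifting of censored times remains one possible reading of the sentence, not something the plan clearly prescribes.

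**What to change.** Replace the sentence on ties in Section 8.1 with:

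*Ties in the Cox models will be handled by the Efron method; observed times will not be altered for the Kaplan-Meier, log-rank or Cox analyses.*

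Name the method explicitly, because Breslow pulled the estimate towards the null on the nominal grid (median HR 0.54 against 0.50). State the unit in which PFS is recorded. An exact-method check for PFS is optional.

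If random tie-breaking is kept, the plan should fix the seed, the amount and its distribution, restrict it to events, and average over a stated number of draws.

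The cost is one sentence and one option in the Cox procedure. It needs no new data and leaves the sample size and the primary analysis unchanged.
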